4. OBJECTIVES

Primary objective

The primary objective of this study is to assess the effectiveness of HCV curative treatments in patients with chronic hepatitis C (CHC), co-infected with HIV in Manipur, India.

Secondary objectives

- a. To describe the demographic, clinical and biological characteristics of patients with chronic hepatitis C and HIV co-infection
- b. To assess the effectiveness of HCV curative strategies in patients with chronic HCV, co-infected with HIV stratified by regimen and by site
- c. To identify risk factors associated with differing virological responses
- d. To assess the safety of HCV treatment
- e. To monitor the safety of HCV treatment in HIV co-infected patients
- f. To document the clinical and biological tolerance of the HCV treatment
- g. To assess the feasibility of HCV treatment
- h. To assess comparative performance of elastography (Fibroscan®) and APRI (AST to Platelet Ration Index), to evaluate liver fibrosis among HIV/HCV co-infected individuals
- i. To describe causes of non-eligibility for treatment
- j. To describe the clinical and biological evolution of co-infected patients, not eligible for HCV treatment
- k. To assess treatment adherence

5. PRESENT KNOWLEDGE AND RELEVANT BIBLIOGRAPHY INCLUDING FULL TITLES OF ARTICLES RELATING TO THE PROJECT

The burden of hepatitis C worldwide is now being recognized as a major public health problem. An estimated 180 million people (~3% of the world's population) are chronically infected with the hepatitis C virus (HCV), responsible for 500,000 deaths each year (1, 2). Two thirds of those infected by Hepatitis C live in Africa or in Asia.

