The individual may withdraw consent at any point during the study with no impact on treatment and care.

¹ Eligibility for study inclusion and HCV treatment are different. The study will also include HCV positive patients who do not receive treatment either due to non-priority of treatment or presence of clinical contraindications. (These patients may receive treatment at a later date). This is intended to fulfil secondary objectives 'i' and 'j'. However patients will receive standard HCV treatment and care in the event of non-eligibility to the study or refusal to participation in the study.

Table 1: Study participant eligibility criteria

	Eligibility criteria for study inclusion	Eligibility criteria for HCV treatment
Inclusion criteria	
 • HIV/HCV co infection independent of the stage of liver disease • Over 18 years of age • HCV viral load greater than 12UI/mL • HIV positive status confirmed by the national and MSF algorithm • Able and willing to provide informed consent • Willing to comply with all study procedures 	Clinical Review 
 • Confirmed HCV infection • HIV infection controlled on ART or asymptomatic HIV infection with CD4 count >500/ μL in the absence of ART • Controlled drug use • Controlled opportunistic infections • Hemoglobin threshold: 9 g/dL
		Psychosocial Review 
 • Adherent to HIV treatment and appointments • Controlled use of substances (if relevant) • No evidence of uncontrolled psychiatric disorder
Exclusion criteria	
 • Individual aged less than 18 years • Individual does not consent to be part of the study. 	Clinical Review 
 • Evidence of hepatocarcinoma • Advanced/terminal heart or pulmonary or renal or other disease • Active, uncontrolled opportunistic Infections • First 3 months of a new ART regimen (unless minor ARV change for toxicity); • Pregnancy or planning pregnancy in following months, unwillingness to use contraception Breastfeeding women.
		Psychosocial Review 
 • Unwillingness of the patient to adhere to HCV treatment & ART • Uncontrolled severe psychiatric disorder. • Unstable substance use

V. Statistical methods to be used

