- Frequency and type of demographic, clinical and biological risk factors associated with treatment outcomes: age , sex, liver fibrosis stage, child pugh score, genotype, clinical symptoms, comorbidities with HBV infection , addiction
- Concerning the safety of HCV treatment: Frequency and type of treatment-related side effects or events that cause modification of dosage of the HCV treatment
- Frequency and type of treatment-related side effects that cause permanent interruption (discontinuation) of the HCV treatment
- Concerning the feasibility of HCV treatment: Proportion of patients included in the cohort but non eligible to treatment at the first assessment, by clinical and biological characteristics, over time (yearly eligibility assessment): HCV viral load, liver fibrosis stage, child pugh score, presence of ascites,HIV viral load
- Frequency and type of demographic, clinical and biological risk factors associated with non-eligibility to treatment: age , sex, fibrosis stage, child pugh score, genotype, clinical symptoms, biological anomalies, comorbidities with HBV infection, addiction
- Frequency of reporting of missed doses by patients

IX. Data management

Data Collection Tools

Paper based questionnaires and lab forms will be used for collection of individual baseline information, clinical evaluation information, laboratory results and treatment information. The different CRFs are presented in Appendix 1 and 2. Other data collection tools may be used in the laboratory. Questionnaires will be pre-tested prior to initiation of data collection. Study forms will be linked through unique study numbers assigned to study participants. Personal identifier information will be recorded on separate forms, and will be kept separately to maintain confidentiality.

Listing of data collection questionnaire (Appendix 1 & 2):

- Baseline information
- Consultation form
- Comorbidities form
- Biological form

- Adverse Events form

In case of adverse events, specific reports will be filled, initial and follow up reports (Appendix 3).

Prior to the inclusion in this cohort, the patient may be under medical follow up for his HIV and / or HCV care. These data are collected on different tools. Some information would be used for this study. As example, the CD4 count at enrolment will be found in the HIV database used in the HIV care facility. The source of the data is specific to each site. The data will be reported to the HCV database.

Data Management and Monitoring

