250_ New Test results (bio or others)	 Yes  No  DK	if Yes: To fill the Lab Form

Pt file N° _____ Visit N°: ____ Name of interviewer: _____	Data clerk Initials: _____ Date data entry: ____ - ____ - ____ (dd-mm-yyyy)
--	--

DOCTOR: HIV Care follow-up	
260_ Is the patient HIV positive	 Yes  No  DK If No or DK, skip to question 270
261_ CURRENT WHO staging (Site) _____	 DK
262_ HIV consultation outcome:	
 Pre ART (skip to 270)	 ART Initiation
 Continuation same dose/ regimen (skip to 270)	 Modification dose/regimen
 Discontinuation due to adverse event (skip to 270)	 Stop for other reasons  (skip to 270)
263_ If HIV Treatment initiation or modification, complete with name and dosage of the new regimen.	
 DK	
Drug _____	Dosage _____  DK (dosage not entered)
Drug _____	Dosage _____  DK (in the database)
Drug _____	Dosage _____  DK
Drug _____	Dosage _____  DK

DOCTOR: CONSULTATION DECISION	
270_ Is the patient eligible for the HCV treatment or currently under treatment?	
 Not assessed /pending results (skip to 280)	 Eligible /or already under treatment (skip to 272)
 Not eligible	 Follow up after treatment (skip to 280)
271_ Reasons not eligible currently for treatment (after skip to 280)	
 Due to ineligible liver stage	 Patient's unwillingness to start
 Due to liver decompensation	 Contraindication to treatment
 Pregnancy/breastfeeding	 Others: (Clinical Case Review priority)
272_ Decision for treatment or continuation of care	
 Waiting List (skip to 280)	 Initiation (skip to 274)
 Continuation same dose	 Modification dose due to weight change

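### A patient who meets the treatment criteria but is not started can be coded as either not eligible or eligible, so two feasibility endpoints depend on the box ticked

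*Protocol*

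**What the plan says.** **Who is included.** Footnote 1 (Protocol section 6, Sampling design) separates eligibility for the study from eligibility for treatment. It says the study also takes in HCV-positive patients who "do not receive treatment either due to non-priority of treatment or presence of clinical contraindications", and adds: "This is intended to fulfil secondary objectives 'i' and 'j." Objective i is "To describe causes of non-eligibility for treatment". Objective j is "To describe the clinical and biological evolution of co-infected patients, not eligible for HCV treatment".

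**What makes a patient eligible for treatment.** The right-hand column of Table 1 lists clinical and psychosocial criteria. None refers to priority, fibrosis stage or decompensation by name.

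**How status is recorded.** CRF2 item 270 asks: "Is the patient eligible for the HCV treatment or currently under treatment". A tick at not eligible leads to item 271, where the reasons include ineligible liver stage, liver decompensation and "Others: (Clinical Case Review priority)". A tick at eligible skips item 271 and goes to item 272, "Decision for treatment or continuation of care", whose first option is Waiting List. That option skips onward without asking why.

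**What is reported.** Section VIII lists "Proportion of patients included in the cohort but non eligible to treatment at the first assessment", with yearly reassessment. It also lists risk factors for non-eligibility, with fibrosis stage and Child-Pugh score among them. Neither endpoint is tied to a CRF item.

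**The concern.** Take a patient who satisfies every Table 1 treatment criterion but is held back because others come first. By Table 1 the patient is eligible. By footnote 1, read with objectives i and j, the patient belongs to the non-eligibility analysis. CRF2 can accommodate either answer, and nothing in the protocol says which to use.

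The numerator of the non-eligibility proportion, and the outcome in the risk-factor model, then depend partly on form-filling habit. Data from three sites are merged into one dataset, so a difference in habit between sites would look like a difference in eligibility. The two kinds of untreated patient may also differ clinically. If those who fail a criterion tend to be sicker and those deferred tend to have milder disease, pooling them blurs the association with fibrosis that the endpoint is meant to describe.

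**Working it through.** **1. The passages side by side, for a patient deferred only for priority**

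| Source | Status implied |
|---|---|
| Table 1 | Eligible: no criterion is failed |
| Footnote 1 with objectives i and j | Part of the non-eligibility analysis (by inference) |
| CRF2 items 270 and 271 | Not eligible, reason Others / Clinical Case Review priority |
| CRF2 items 270 and 272 | Eligible, Waiting List, no reason recorded |

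Liver stage and decompensation show the same mismatch: both are reasons in item 271, and Table 1 names neither. Tables 2 and 3 give regimens for patients without and with cirrhosis, and note 8 to Table 3.0 provides for on-treatment blood counts in decompensated cirrhosis.

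**2. The denominator.** The protocol's cohort size reproduces: 1600 × 0.27 × 0.80 = 345.6, stated as 345.

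**3. Effect on the proportion.** Let c be the share who fail a treatment criterion, d the share who meet the criteria but are deferred, and f the fraction of deferred patients ticked as not eligible. The reported proportion is

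P = c + f × d,

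which runs from c (f = 0) to c + d (f = 1). Two sites with the same case mix but different habits differ by (f₁ − f₂) × d. This needs no assumed value.

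The protocol gives neither c nor d. With c assumed to be 10%:

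| d (assumed) | P if f = 0 | P if f = 1 | Expected count of 345 |
|---|---|---|---|
| 5% | 10% | 15% | 34.5 vs 51.75 |
| 10% | 10% | 20% | 34.5 vs 69 |
| 20% | 10% | 30% | 34.5 vs 103.5 |
| 30% | 10% | 40% | 34.5 vs 138 |

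For scale, the standard error at 10% is √(0.10 × 0.90 / 345) = 1.6 points, giving a 95% interval of about 6.8% to 13.2%.

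**4. Effect on the fibrosis association (illustration only; every input is assumed).** Suppose 20% of F4 and 8% of non-F4 patients fail a criterion. With deferred patients coded eligible, the odds ratio for F4 is (0.20/0.80) / (0.08/0.92) = 2.9. Now code as not eligible a fraction w of otherwise eligible patients.

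| w | Deferral in non-F4 only: non-F4 rate 0.08 + 0.92w | OR | Deferral equal in both groups: F4 rate 0.20 + 0.80w | OR |
|---|---|---|---|---|
| 10% | 17.2% | 1.20 | 28.0% | 1.87 |
| 25% | 31.0% | 0.56 | 40.0% | 1.48 |
| 40% | 44.8% | 0.31 | 52.0% | 1.33 |

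With deferral confined to non-F4, reversal needs 0.08 + 0.92w > 0.20, that is w above about 13%. With deferral equal in both groups, the association weakens but does not reverse. A second assumed set (15% vs 8% failing a criterion, deferral in 5%, 10% or 25% of all non-cirrhotic patients and in no cirrhotic patients) moves the odds ratio from 2.03 to 1.18, 0.80 or 0.36.

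**The case against.** **The conflict is partly inferred.** Footnote 1 never calls non-priority patients non-eligible; that follows from its reference to objectives i and j. Waiting List does not name priority either. The two CRF routes might describe different states: a case review that decided against treatment for now, and a patient cleared but not yet started, for instance during the pretreatment counselling sessions that CRF2 records. This stands as a possible reading. But the protocol does not state it, and Waiting List is the form's only place for an eligible patient who has not started.

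**An analysis plan could sort it out.** In part. Item 271 has separate boxes for contraindication, decompensation, liver stage, pregnancy or breastfeeding, and unwillingness, and Waiting List is distinct from all of them. But priority shares one box with Others. Table 1 failures without their own box, such as the haemoglobin threshold, adherence to HIV treatment or the first months of a new ART regimen, could be placed there too. Waiting List carries no reason. A later rule cannot fully separate what was entered together.

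**Stronger readings.** A reader might infer that the fibrosis association will reverse. The documents do not support this: they state no prioritisation rule, no deferral share and no contraindication rate, and reversal requires deferral to be both common and concentrated in milder disease. A reader might also infer that outcomes in untreated patients are compromised throughout. They are not: mortality is reported by whether treatment was initiated, as is the proportion initiating, and neither changes with the box ticked.

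**Conclusion.** Treatment eligibility is not coded consistently between footnote 1, Table 1 and CRF2 items 270–272. Two secondary feasibility endpoints are exposed: the proportion non-eligible at first assessment, and the risk factors for non-eligibility. The proportion moves by exactly the share of all patients who are deferred and coded differently. That size cannot be fixed from the protocol; under the assumed shares above it is 5 to 30 points. The association with fibrosis could weaken, and under some assumptions reverse, if deferral falls mainly on milder disease; this remains illustrative.

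The primary endpoint (SVR12 among patients who initiated treatment), the ITT population, the sample size and mortality by treatment initiation are unaffected. The point is confined to secondary endpoints. It is worth correcting early because the weakness lies in data capture.

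**What to change.** - **Reconcile the passages.** Bring footnote 1, Table 1 and CRF2 items 270–272 into agreement, including the liver-stage and decompensation reasons in item 271. Which clinical rule applies is for the investigators; this review takes no position on it.
- **One place, one code.** Record patients who meet the treatment criteria but have not started (non-priority or waiting list) in a single place on CRF2, with a code of their own that is not shared with Others.
- **Report separately.** For the two feasibility endpoints in section VIII and for objectives i and j, present this class apart from patients who fail a treatment criterion.

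The cost is one relabelled option and the matching text edits. Because the form is already in use and feeds an existing database, a short note is needed on how earlier records are mapped; those in the shared Others box may not be separable. Compared with counting deferred patients as not eligible, the headline non-eligible proportion will be smaller, with the deferred proportion shown beside it.

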2. PROJECT SITES

- a. Doctors without Borders Clinic, [name].
- b. Doctors without Borders Clinic [name]
- c. Doctors without Borders Clinic, [name]

3. BACKGROUND & RATIONALE FOR THE STUDY AND ITS APPLICATION WITH RESPECT TO THE PROGRAMME PRIORITIES UNDER NACP-IV.

INTRODUCTION

Médecins Sans Frontières (MSF) has been active in Manipur state since 2004. MSF has ART centres in Churachandpur, Moreh and Chakpikarong providing care and treatment to over 1600 people living with HIV/AIDS (PLWHA). MSF has a Public Private Partnership (PPP) with the National AIDS Control Organisation (NACO). Both parties signed an MOU in which it was agreed to set up a collaborative ART project between NACO and MSF that would seek to be a model for high quality provision of ART and associated healthcare and medical management of PLWHAs in its sites in India. As part of this commitment to care, MSF commenced hepatitis C (HCV) treatment for HIV co-infected individuals in July 2015 in Churachandpur.

The rapidly evolving HCV landscape, including new DAA based regimens, provides novel treatment options and opportunities to treat patients successfully, with fewer side effects and simplified surveillance in low resource settings. The aim of this study is to assess the effectiveness and safety of chronic HCV treatment amongst HIV positive co-infected patients

receiving treatment in accordance with current WHO and other International treatment protocols and guidelines, within real world settings.

A prospective longitudinal cohort study was chosen to support the monitoring of the introduction of these new regimens and contribute to post licensure surveillance. An important caveat to note is that this study is in no way a Phase four clinical trial or a pharmaco-vigilance study. The methodology described is in accordance with an observational study of a cohort of patients under HCV treatment in the MSF ART centres and analysis of routinely collected clinical data.

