6. DETAILED RESEARCH PLAN

METHODOLOGY

I. Study Design

The study will be a prospective longitudinal cohort study, which will monitor the diagnosis, treatment and follow-up of the HIV patients identified with a chronic hepatitis C within 3 clinic sites in Manipur; Churachandpur, Chakpikarong and Moreh.

The analysis of routinely collected clinical data will facilitate the assessment of the effectiveness of HCV treatment among patients with chronic hepatitis C, co-infected with HIV, from time of confirmation of their HCV Viral load until SVR12, death, lost to follow up, medical decision to exit the study or transfer out, whichever comes first.

The study will assess implementation of new recommended HCV-curative regimens in real world settings, not specific new drugs. The specific treatment regimens used, including new DAAs, will be selected in accordance with current WHO, international and national recommendations and protocols (18-20). Of the new DAA's, only drugs registered and available in India will be used in accordance with international and national recommendations and protocols.

II. Study population

The study population will include HIV infected patients from Manipur state diagnosed with chronic hepatitis C (viral load HCV positive) meeting eligibility criteria. These patients will be directly identified in the MSF sites.

III. Sample size

The sample will exhaustively include all patients meeting the inclusion criteria in each site for a period of two years. Currently MSF, in collaboration with NACO has approximately 1600 adult patients being actively followed up for HIV care within Manipur. The overall rate of HIV-HCV co-infection, based on HCV serological screening performed to date is approximately 27%. Assuming 80% of serologically positive patients have chronic hepatitis C, the minimum sample size expected for this study will be 345 patients.

IV. Sampling design

The sample will exhaustively include all patients meeting the inclusion criteria in each site for a period of two years.

Inclusion and Exclusion criteria:

When the results of VL tests become available, all patients over 18 years will be invited to participate in the study, if they fulfill eligibility criteria. Inclusion is not linked with eligibility for HCV or HIV *treatment*. A criterion of non-eligibility to treatment is not considered as inclusion or exclusion criteria for study participation¹.

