Demographic and baseline characteristics of the patients will be described using summary statistics (mean with their 95% CI or median with inter-quantile intervals for continuous data; frequency and proportion for categorical data). It will include (but not be restricted to): - age - sex – treatment received - clinical signs at inclusion, haemoglobin and other biological measures at inclusion.

Depending of the distribution of the data, different tests and reports of results will be provided. Distributions of categorical variables between two groups will be compared with the Fisher's exact test or chi-squared. Comparisons of continuous variables will be performed with a 2-sample t-test when the variable shows a normal distribution; otherwise, a Wilcoxon rank sum test will be performed.

Risk factors associated with the different outcomes will be assessed using univariate and multivariate models. Epidemiological and clinical relevant variables will be included in the multivariate model to obtain an adjusted measure of association.

To assess the APRI performance, compared to Fibroscan®, for assessment of liver fibrosis among HIV/HCV coinfecting individuals, sensitivity, specificity, negative predictive value, positive predictive value will be computed, across liver fibrosis scores.

We will use an alpha level of 5% for all statistical tests. All statistical tests will be two-sided. All efficacy endpoints will be analyzed on the intent-to-treat (ITT) population during the cohort study (every year). The ITT population will include all subjects who were initiated under treatment (at least one prescription of HCV treatment).

Analyses will be performed using STATA, version 13 (StataCorp, College Station, Texas).

VI. Tools

Demographic and clinical data is currently collected via case reporting forms (CRFs) and laboratory forms. Data is collected on: individual baseline information, clinical evaluation information, laboratory results and treatment information. The CRFs are presented in Appendix 1-4. (All forms are currently being used for recording clinical management of new HCV patients entering treatment). De-identified data is entered in to an electronic database and used for reporting and monitoring and evaluation of HCV treatment activities.

Study participants will be linked through unique study numbers assigned to study participants. Personal identifier information will be recorded only on CRFs, and will be kept separately to maintain confidentiality.

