<http://www.ipc.gov.in/PvPI/ADRReportingForm.pdf>. All AE or AR considered as serious AE or leading to a change in the treatment, from the date the patient starts the HCV treatment, during the entire treatment follow-up, and up to four weeks after the intake of the last regimen drug should be reported. In addition, serious AE that occur after this period and during the post-treatment follow-up should be reported if the event is suspected to be related to any of the drugs included in the regimen. The decision to postpone, modify or to interrupt/discontinue the regimen will be left at the discretion of the clinical team following discussion with the study principal investigators and with the medical HCV referent of the

section. For all AEs, patients will receive the best care available and will be followed up until resolution.

List of potential adverse events and their management are provided in appendix 6

Medical advisory panel

The study is supported by a medical co-ordinator, study principal investigator, based in the Delhi Co-ordination of MSF. Regular program committees will be held to discuss medical or program issues. The program committee also has a access to a team of experts, including clinicians and virologists specialized on HCV treatment, who will advise on the individual patient management and treatment decisions in case of specific conditions. The program committee and the experts will have access to coded clinical and biological data collected during the study, as appropriate, from patients requiring specialized care.

Standardized documents with the required information will be used. The review and patient decision will also involve closely the MSF medical team and medical coordinator in each study site. Recommendations will be based on patient's records data, on current international and national recommendations and on the availability of access to drugs in the country.

VIII. Study Outcome Measures

The primary endpoint is the proportion of patients with sustainable viral response at 12 weeks, among patients who initiated HCV treatment (irrespective of regimen).

The endpoint will be plasma HCV-RNA response at week 12 after end of treatment (EoT). Treatment success is defined as viral load as either undetectable or below a concentration of 12UI/mL Treatment failure is defined as either a detectable viral load 12 weeks after cessation of treatment, death or loss to follow-up, medical decision to exit the study or transfer-out.

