A trained clinician/counselor will administer the information sheet verbally, encouraging questions. When it is deemed the subject has a good understanding they will be asked to sign the consent form. The subject will sign the informed consent document prior to any study-related analysis of their data. Subjects will be given the opportunity to discuss the study with their surrogates or think about it prior to agreeing to participate. The participant, if functionally illiterate, may sign the consent by marking with a thumbprint on the signature line. The presence of a witness who will also have to sign the document will also be encouraged. The subject may withdraw consent at any time throughout the course of the study. A copy of the signed informed consent document will be given to subjects for their records. The rights and welfare of the subjects will be protected by emphasizing to them that the quality of their clinical care will not be adversely affected if they decline to participate in this study.

XII. Timelines

The study has an estimated start date of December 2016, and with the end of inclusions being December 2018. Table 2 provides a breakdown of the study timetable for the Manipur sites.

Table 4: Study Timeframe

Activities	Time
Protocol development and submission to MSF Ethical Committee	Jan 2016-April 2017-
National Protocol developments and submission to NACO	April 2016 – Nov 2016
Field preparation and pilot study	Nov-Dec 2016
Recruitment	May 2017 to May 2019
Follow-up patients	May2017 toAug 2019
Field data management	May 2017 to Aug 2019
Regular Data analysis and Monitoring_ interim reports	May 2016 to Aug 2019
Final report (including outcomes)	Dec 2019
External communication	Jan 2020

7. FACILITIES IN TERMS OF EQUIPMENT, ECT, AVAILABLE AT THE INSTITUTION / ORGANISATION FOR THE PROPOSED INVESTIGATION

The treatment activities on which this observational study will be performed are on-going programmatic activities within the MSF clinics located in Churachandpur, Chakpikarong and Moreh. Within these locations MSF in partnership with NACO, operate as outpatient facility with associated on-site laboratory capacity. Each of these laboratories is capable of performing routine biochemistry, haematology, CD4 counts, serological testing HIV / HCV / HBV / Syphilis and Microscopy. Each also has a GeneXpert machine. In addition a mobile Fibroscan machine is present and can be moved between these sites.

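### The protocol does not rule out inclusion after the first HCV prescription, so the primary SVR12 proportion is open to selection bias of unknown size, and the follow-up clock can start before anyone could consent

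*Protocol*

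**What the plan says.** - **Population.** Section 6.V: "The ITT population will include all subjects who were initiated under treatment (at least one prescription of HCV treatment". No date and no link to consent or inclusion is given.
- **Primary endpoint.** Section 6.VIII takes the SVR12 proportion "among patients who initiated HCV treatment (irrespective of regimen", and counts as failure, besides a detectable viral load, "death or loss to follow-up, medical decision to exit the study or transfer-out".
- **Calendar.** Section 3 (Introduction): "MSF commenced hepatitis C (HCV) treatment for HIV co-infected individuals in July 2015 in Churachandpur". Section 6.VII dates viral-load confirmation from 2015. Section 6.XII gives an estimated study start of December 2016 in the text, but recruitment "May 2017 to May 2019" in Table 4.
- **Eligibility.** Table 1 asks for an HCV viral load above 12 IU/mL without saying when it is measured. Its study-inclusion column contains no exclusion for current or past HCV treatment. Sections 6.III and 6.IV make the sample exhaustive.
- **Earlier care.** Section 6.IX: "Prior to the inclusion in this cohort, the patient may be under medical follow up for his HIV and / or HCV care".
- **Consent.** Section 6.XI(e): "The subject will sign the informed consent document prior to any study-related analysis of their data". Section 6.VII places the initial interview after consent, at the inclusion visit.
- **Clock.** Section 6.I observes patients "from time of confirmation of their HCV Viral load until SVR12" or an earlier exit.

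**The concern.** The programme had been treating patients for well over a year when inclusions were due to open. A patient prescribed before that date can enter the cohort only if still alive and in care when invited. One who started on the same day and then died, defaulted or was transferred cannot enter. The endpoint definition treats those exits as failures, so the second patient is a failure that the study cannot observe. If both kinds of starter exist and the first kind is counted, being in the primary denominator depends partly on not having failed.

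The same gap affects the clock. Time between viral-load confirmation and inclusion is time in which no included patient can have died or defaulted. Counting it lowers mortality and pre-treatment default in the cohort.

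This is not a detail to leave to an analysis plan, because the protocol itself fixes the population, the denominator and the start of follow-up.

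**Working it through.** **1. The plan's own figure.** Section 6.III: 1600 × 0.27 × 0.80 = 345.6, stated as 345. It reproduces. It is the whole expected pool of co-infected patients in care, with nothing deducted for those treated since 2015. It includes patients who will not be treated, so the number of treatment starters will be smaller.

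**2. The gap in time.** July 2015 to December 2016 is 17 months; July 2015 to May 2017 is 22 months.

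**3. If a past viral load qualifies (left truncation).** Let p be the true SVR12 among all starters, f the share of starters who began before inclusion, and e the share of those who died or left before they could be included. All of the latter are failures, so

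observed SVR12 = p / (1 − f·e).

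The protocol gives none of p, f or e; the values below are assumptions. Overstatement in percentage points:

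| p | f | e = 0.02 | e = 0.05 | e = 0.10 |
|---|---|---|---|---|
| 0.80 | 0.1 | 0.16 | 0.40 | 0.81 |
| 0.80 | 0.3 | 0.48 | 1.22 | 2.47 |
| 0.80 | 0.5 | 0.81 | 2.05 | 4.21 |
| 0.90 | 0.1 | 0.18 | 0.45 | 0.91 |
| 0.90 | 0.3 | 0.54 | 1.37 | 2.78 |
| 0.90 | 0.5 | 0.91 | 2.31 | 4.74 |

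Example: 0.90 / (1 − 0.3 × 0.05) = 0.90 / 0.985 = 0.914. If all 345 were starters, the missing failures would number from 345 × 0.1 × 0.02 = 0.7 to 345 × 0.5 × 0.10 = 17.

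**4. If viral load must be detectable at consent.** Let v be the share of earlier starters still viraemic at consent and s their SVR12. Then

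observed = [(1 − f)p + f·v·s] / [(1 − f) + f·v],

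so bias = f·v·(s − p) / [(1 − f) + f·v].

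This is negative whenever s is below p. With the same p and f, and (v, s) set to (0.05, 0), (0.10, 0) or (0.10, 0.5), it runs from −0.3 points (p = 0.80, f = 0.1, v = 0.10, s = 0.5) to −8.2 points (p = 0.90, f = 0.5, v = 0.10, s = 0). If the viraemic patients had only just started and s is close to p, it is near zero.

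**5. Scale.** At n = 345 the 95% half-width is 1.96 × √(p(1 − p)/345): 4.2 points at p = 0.80 and 3.2 points at p = 0.90. It is wider with fewer starters. The bias may be negligible or may exceed the half-width, and a larger sample would not reduce it.

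**6. The clock.** If g is the time from confirmation to inclusion and h the time from inclusion to the end of follow-up, a constant event rate λ is estimated as λ·h/(g + h) when the clock starts at confirmation. For a patient confirmed by July 2015 (an assumption; the protocol says only during 2015), g is at least 17 or 22 months.

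**The case against.** The strongest reply is that the protocol describes enrolment before treatment. Section 6.IV invites patients as viral-load results arrive. Section 6.VII offers the study to those with detectable virus, explains the regimen to them, and takes consent before the inclusion interview. Table 3.0 runs from baseline through a pre-treatment visit to treatment weeks. The sentence in section 6.IX introduces data sources, and its example is a CD4 count; HCV care may also mean diagnosis or a waiting list. The study is descriptive, with no SVR12 threshold, so no test decision turns on a few points.

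Much of this stands, and it rules out three stronger readings.

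- A reader might infer that the protocol plans to enrol patients already on treatment. No sentence says so.
- A reader might infer from section 6.XI(e) that consent is needed only before analysis. Section 6.VII places consent before the inclusion interview, so the sentence on analysis is a minimum safeguard and does not define when enrolment happens.
- A reader might infer that SVR12 is biased upward as a matter of fact. If the viral load must be current, patients suppressed on treatment or cured are largely shut out, while earlier starters who remain viraemic can enter. The direction can then reverse.

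What the reply does not remove is the gap itself. Results from 2015 and 2016 were already available when inclusions opened, and no rule covers those patients. The sample is meant to be exhaustive over a pool that contains them. Read literally, any earlier prescription meets the population definition, and CRF1 items 121 to 124 expect some patients to have had HCV treatment before.

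**Conclusion.** The concern holds as a conditional one. The protocol permits, without stating it, inclusion after the first prescription, and its population rule would count such patients. The primary proportion is therefore open to selection bias whose size cannot be derived from the protocol. Under left truncation it is upward, about 0 to 5 points for p of 0.80 to 0.90, f of 0.1 to 0.5 and e of 0.02 to 0.10. If viral load must be detectable at consent, it may be downward. If no patient was prescribed before inclusion (f = 0), it is zero.

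The immortal-time point is separate. It concerns cohort mortality and pre-treatment default, and arises for anyone confirmed before being able to consent, treated or not. Its size depends on a gap that the protocol does not describe.

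This should be fixed, because the primary population has two tenable readings with biases that can run in opposite directions and a short clarification settles both. It does not invalidate the design.

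**What to change.** - **Table 1:** state that the qualifying viral load is the pre-treatment one, and whether patients who have already received HCV treatment may be included.
- **Sections 6.V and 6.VIII:** limit the primary ITT set to participants whose first HCV prescription in the programme falls on or after the inclusion visit. Report participants already treated at inclusion separately, outside the primary proportion. A count of earlier starters who died or left before they could be invited would show how much was missed.
- **Section 6.I:** start follow-up for mortality and default at the later of viral-load confirmation and inclusion.

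For the inclusion date use the CRF1 interview at the inclusion visit, because question 21 records consent only as Yes/No/DK, without a date. For the first prescription use the date of the CRF2 visit at which item 272 records initiation. The cost is protocol wording and a somewhat smaller primary denominator; on these dates no new data item is needed.
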